7.1.3. Unexpected Adverse Event

An AE or suspected adverse reaction is considered "unexpected" if it is not listed in the Investigator's Brochure or is not listed at the specificity or severity that has been observed; or, is not consistent with the risk information described in the protocol or elsewhere. For example, under this definition, hepatic necrosis would be unexpected (by virtue of greater severity) if the Investigator's Brochure referred only to elevated hepatic enzymes or hepatitis. Similarly, cerebral thromboembolism and cerebral vasculitis would be unexpected (by virtue of greater specificity) if the Investigator's Brochure listed only cerebral vascular accidents.

"Unexpected," as used in this definition, also refers to AEs or suspected adverse reactions that are mentioned in the Investigator's Brochure as occurring with a class of drugs or as anticipated from the pharmacological properties of the investigational therapy, but are not specifically mentioned as occurring with the investigational therapy.

7.1.4. Adverse Event Reporting Period

The adverse event reporting period begins from the date of the first dose of study drug to 28 days following the last dose of study drug.

7.1.5. Recording of Adverse Events

Each AE should be recorded in standard medical terminology on the AE CRF module. Whenever possible, the AE should be evaluated and reported as a diagnosis rather than as individual signs or symptoms. For example, cough, runny nose, sneezing, sore throat, and head congestion should be reported as 'upper respiratory infection'. If a definitive diagnosis is not possible, the individual signs and symptoms should be recorded. Dates of

start (onset) and stop (recovery), action taken, and outcome will be recorded in the AE CRF module.

All clinically significant abnormal changes in laboratory parameters will be recorded as an AE on the AE module, with the following exceptions: clinically significant abnormal laboratory changes determined to be related to the study condition and concomitant conditions, e.g., diabetes, of which the investigator was previously aware and that have not worsened.

The investigator will evaluate all AEs with regard to maximum intensity and relationship to study drug, as follows.

7.1.5.1. Maximum Intensity

Maximum intensity should be assigned using one of the severity grades as outlined in the National Cancer Institute Common Terminology Criteria for Adverse Events (NCI CTCAE v4.0); if the AE is not specifically listed in CTCAE v4.03, use the following grades:

- Grade 1: mild
- Grade 2: moderate
- Grade 3: severe
- Grade 4: life-threatening or disabling
- Grade 5: death

7.1.5.2. Relationship to Study Drug

The degree of certainty with which an AE is attributed to study drug (or alternative causes, e.g., natural history of the underlying diseases, concomitant therapy, etc.) will be determined by how well the event can be understood in terms of known pharmacology of the study drug and/or reactions of similar nature previously observed with study drug. Each AE will be assigned one of the following five categories:

- *Not related*: There is not a temporal relationship to the study drug (e.g., too early, too late), or there is a reasonable causal relationship to another drug, concurrent illness, or circumstance.
- *Unlikely related*: There is a temporal relationship to study drug, but there is not a reasonable causal relationship between the time of study drug administration and the AE (i.e., it is doubtful the AE is related to the study drug); could be reasonably explained by other factors, including underlying disease, complications, concomitant drugs, or concurrent treatment.
- *Possibly related*: There is a reasonable temporal sequence from time of study drug administration (e.g., occurred in a time frame relevant to study drug dose); or for which the possibility of the study drug being the causative factor (e.g., existence of similar reports attributed to the study drug; reactions attributable to the pharmacological effect) could not be excluded, although other factors such as

underlying disease, complications, concomitant drugs, or concurrent treatment are presumable.

- *Probably related:* There is a reasonable temporal sequence from time of study drug administration; and for which the possibility of factors other than the study drug administration, such as underlying disease, complications, concomitant drugs, or concurrent treatment, could not be excluded as the cause.
- *Definitely related:* Follows a clear temporal sequence from time of study drug administration; could not be possibly explained by the known characteristics of the subject's clinical state, environmental or toxic factors, or other modes of therapy administered to the subject; follows a response pattern known to be associated with study drug administration.

7.1.6. Most Commonly Expected Adverse Events

The most commonly reported adverse events in a Phase 2 study of 165 subjects with hematologic malignancies at doses of 14 – 600 mg/m² BID were nausea (9%), anorexia (7%), rash (4%), vomiting (4%), abdominal discomfort (2%) and pruritis (1%). Changes in laboratory values were elevated ALT (10%), AST (9%), thrombocytopenia (5%), decreased hemoglobin (2%), neutropenia (2%) and decreased bilirubin (2%). All other adverse events were reported at incidences of 1% or less. Laboratory changes were reported as temporary, ≤ Grade 2, and reversible. For bone marrow changes, nadir was reached in 2 -3 weeks for neutropenia, 3 weeks for platelets and 5 weeks for hemoglobin. Recovery from nadir values was approximately 2 weeks for all parameters.⁷

7.1.7. Adverse Event Reporting

Each AE is to be reported by the investigator as serious or non-serious according to the definitions in **Section 7.1.2** above. This classification determines the regulatory reporting procedures to be followed as described in **Table 6**.

Table 6. Reporting Guidelines for Adverse Events

Gravity of AE	Reporting Time to FPHU/Westat	Type of Report
Serious	Within 24 hours after the site becomes aware of the event	Initial SAE Report
Non-Serious	Per AE CRF module	Completed AE CRF Module

Any SAE, regardless of relationship to investigational therapy that occurs within 28 days following the last dose of study drug must be reported to the Medical Monitor within 24 hours after the site becomes aware of the event. The investigator is encouraged to discuss with the Medical Monitor any adverse experiences for which the issue of reportability is unclear or questioned. The initial report should be followed by submission of a more detailed SAE Report when follow-up information is available.

If the SAE occurs more than 28 days after the last dose of study drug, SAEs should be reported **only if considered related to FF-10501-01**. In the event of subject death, the reason for death should be recorded as the SAE, with 'death' recorded as the outcome on the SAE CRF module.

The SAE also will be recorded as an AE on the AE CRF module. Note: the SAE Report is different from the AE CRF. In areas of both forms where the same data are reported, the forms will be completed in a consistent manner. For example, the same term should be used for the AE on both forms, with the same start and stop dates, action taken, outcome, etc. A checkbox on the AE CRF module for whether the AE resulted in an SAE, will link the two types of report for a given event.

An SAE Report should be prepared with as much available information concerning the event as possible so that a written report can be filed with the appropriate regulatory authorities. If causality cannot be determined definitively at the time of the SAE occurrence, it is important to notify FPHU/Westat within the timeline stated above, and to attribute the relationship as 'Not Assessable' (only applicable for the initial SAE Report). When new significant information is obtained and the outcome and attribution of the event is known, the investigator will communicate this in a follow-up SAE Report. This relevant information will be provided in a timely manner to allow reporting to regulatory authorities within the required reporting period. Any SAE follow-up information requested by FPHU/Westat should be provided in a timely manner.

As necessary, the SAE Report should be accompanied by relevant pages from the CRFs, e.g., medical history, AEs, concomitant medications. Additional information may be requested by FPHU/Westat in an expedited manner to ensure that the initial reporting of the SAE made to the regulatory authorities complies with the required time frame. FPHU/Westat may be required to collect and report additional information to the regulatory authorities in a follow-up report, containing a final evaluation of the event, including copies of hospital reports, autopsy reports, or other relevant information.

7.1.8. Adverse Event and Serious Adverse Event Follow-Up

All AEs and SAEs should be followed until resolution, return to baseline, or until the point it is deemed that further recovery is unlikely. All measures required for AE management and the ultimate outcome of the AE will be recorded in the source document and AE CRF module.

7.1.9. Ongoing Safety Evaluation

A study safety evaluation will be conducted on a regular (monthly) basis by teleconference. Dose exposure, dose-limiting toxicity, AE/SAE profiles and clinical laboratory abnormalities, and other safety measures will be reviewed during each convened meeting. Subject accrual will not be interrupted during the regular scheduled safety evaluations. These discussions will be led by the FPHU Medical Monitor and clinical site investigators.

7.1.10. Clinical Laboratory Tests

Clinical laboratory tests include hematology, serum chemistry, urinalysis and bone marrow aspirate (**Table 7**).

Table 7. Clinical Laboratory Parameters

Hematology	Serum Chemistry	Urinalysis	Bone Marrow Aspirate
Red blood cell count	Serum creatinine	pH	Marrow blast percent
Hemoglobin	BUN	Blood	Marrow cellularity percent
Hematocrit	Glucose (non-fasting)	Nitrites	Cell line maturation
White blood cell count	Albumin	Glucose	Auer rods
Differential:	AST	Ketones	Dysplasia
Neutrophils	ALT	Leucocytes	Cytogenetic abnormalities
ANC	LDH	Protein	
Lymphocytes	Total bilirubin	Microscopic examination	
Monocytes	Total protein		
Eosinophils	Alkaline phosphatase		
Basophils	Calcium		
Platelets	Phosphorus		
Blasts percent	Magnesium		
	Sodium		
	Potassium		
	Chloride		
	Bicarbonate		

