1. INTRODUCTION

1.1. FF-10501-01 Background

FF-10501-01 (5-hydroxy-1*H*-imidazole-4-carboxamide 3/4 hydrate), is the 3/4 hydrate of FF-10501, an oral antimetabolite anticancer agent. It is a potent competitive inhibitor of inosine 5'- monophosphate dehydrogenase (IMPDH), a key enzyme involved in de novo purine synthesis, and inhibits deoxyribonucleic acid (DNA) synthesis of guanine monophosphate from xanthosine monophosphate. The chemical structure and mechanism of action of FF-10501 is depicted in **Figure 1**.

[figure not shown]

Figure 1. FF-10501 Structure and Mechanism of Action

FF-10501-01 contains the same active pharmaceutical ingredient as SM-108, a compound discovered in the 1980s and developed through Phase 1 and 2 clinical studies by Sumitomo Chemical Co. FF-10501-01 drug substance is manufactured identically to SM-108, but the synthetic process was improved to increase the purity of FF-10501-01, which ensures better drug substance stability and a more stable FF-10501-01 drug product. SM-108 is the compound designation for studies previously conducted by Sumitomo. FF-10501-01 was used as the test article in all studies conducted under the direction of FUJIFILM.

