1.3.1. Phase 1 Study in Advanced Solid Tumors or Hematologic Malignancies

In a Phase 1 study of oral SM-108 in patients with advanced solid tumors or hematologic malignancies, 73 patients were treated on a 5-day consecutive schedule at doses ranging from 20 to 2500 mg/m².⁵ Adverse events were reported in 23 of 73 patients (31.5%), however a correlation between adverse events and dose was unclear. The maximum tolerated dose (MTD) and doses eliciting dose-limiting toxicity (DLT) were not determined. The most common adverse events reported were gastrointestinal; nausea (11 patients, 15%), anorexia (7 patients, 10%), emesis (5 patients, 7%). Elevated AST (to > 45 U), ALT (to > 50U) and uric acid (to \geq 8 mg/dL) also were noted in some patients. In 31 patients with hematologic malignancies enrolled in the study, 2 of 3 patients with atypical leukemia achieved a complete response, and 2 of 12 patients with acute myeloid leukemia (AML) and 1 of 1 patient with acute lymphocytic leukemia (ALL) achieved a partial response (PR). Mean days to response ranged from 12 to 18 days. No responses were noted in the 42 patients with solid tumors.

A dose-dependent increase in serum levels of SM-108 were observed up to 2000 mg/m²/day, with time to peak serum concentration (T_{max}) of 2 hours at \leq 100 mg/m² and T_{max} of 4 hours at doses \geq 240 mg/m². A total of 40 – 60% of the administered drug was excreted in active form in the urine over 24 hours post-dose, suggesting primary renal elimination.

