1.3.3. Phase 2 Study in Advanced Hematologic Malignancies

A larger Phase 2 study was conducted in patients with advanced hematologic malignancies.⁷ A total of 165 patients were enrolled; 85 had received prior therapy with antimetabolites, including 6-MP or cytosine arabinoside (ara-C). Patients were treated with SM-108 orally, at doses of 70, 200 or 300 mg/m² BID (140, 400 or 600 mg/m²/day). In 39 patients with chronic myelogenous leukemia (CML), 21 had complete responses (CRs) and 6 had PRs for an OR rate of 69%. Among 30 patients with AML, 7 had PRs (23%). Among 36 patients with MDS, 1 had a CR, 12 had PRs for an ORR of 36%. For 13 patients with polycythemia rubra, 4 had CRs and 7 had PRs for an ORR of 84.6%). The RR rate was highest in patients with CML and MDS at doses of \geq 600 mg/m²/day. Clinical responses by dose are described in **Table 1**.

Table 1. Phase 2 Study in Hematologic Malignancies: Clinical Response by Dose

Diagnosis Dose (mg/day)	CML	MDS				Polycythaemia vera	AML	Total (%)
		CMMoL	RAEB	RAEB in T	Total			
< 200			1/2		½		0/2	1/4 (25)
200 to < 400	1/1	1/1	0/1	0/3	1/5	2/2	1/3	5/11 (45.5)
400 to < 600	2/4	0/1	2/7	0/3	2/11	3/3	2/11	9/29 (31)
600 to < 800	20/22	4/7	2/3	2/4	8/14	6/8	2/10	36/54 (66.7)
800 to < 1000	4/11	0/2	0/1	1/1	¼		2/4	7/19 (36.8)
1000 \leq	0/1							0/1
Total (%)	27/39 (69.2)	5/11 (45.5)	5/14 (35.7)	3/11 (27.3)	13/36 (36.1)	11/13 (84.6)	7/30 (23.3)	58/118 (49.1)

The most commonly reported adverse events were gastrointestinal (nausea, anorexia, vomiting, abdominal discomfort; 66%), followed by allergic symptoms (rash, pruritis; 1%). Changes in laboratory values occurred in 30 of 165 (18%) of patients, all were transient/reversible and most were \leq Grade 2. A total of 14 patients (8%) experienced bone marrow suppression (neutropenia, thrombocytopenia, reduced Hb). The nadir was reached in 2 -3 weeks for white blood cell (WBC) count and platelets, 5 weeks for Hb, and recovery from nadir to pre-dose values was approximately 2 weeks (**Table 2**).

Table 2. Phase 2 Study Hematologic Malignancies: Adverse Events in $\geq 2\%$ Patients

Total Number of Patients		165
Number of Patients Reporting (%)	Increased ALT	16 (9.7)
	Nausea	15 (9.1)
	Increased AST	14 (8.5)
	Loss of appetite	11 (6.7)
	Decreased platelet count	8 (4.8)
	Rash	7 (4.2)
	Vomiting	6 (3.6)
	Decreased hemoglobin	4 (2.4)
	Abdominal discomfort	3 (1.8)
	General malaise	3 (1.8)
	Decreased WBC	3 (1.8)
	Increased total bilirubin	3 (1.8)
	Increased GTP	3 (1.8)

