2. STUDY OBJECTIVES

2.1. Primary Objective:

- To determine the safety and tolerability in subjects who receive FF-10501-01 for the treatment of advanced hematologic malignancies

2.2. Secondary Objective:

- To determine the overall response rates
- To evaluate the proportion of subjects who achieve hematologic improvement in peripheral blood or bone marrow blast count
- To evaluate progression-free survival (PFS)
- To evaluate overall survival (OS)
- To evaluate the pharmacokinetics of FF-10501 and M1
- To evaluate the xanthosine monophosphate (XMP) as a pharmacodynamic marker

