Appendix D. Schedule of Study Procedures

Study Activity	Screening ^a	Treatment Cycle 1					Treatment Cycles after Cycle 1		Progression or Relapse	End of Study ^o	Long-Term Follow-Up ^p
		Day 1	Day 8 ^k	Day 15 ^k	Day 22 ^k	End of Cycle 1 ^l	Day 1 ^m	End of Cycle 3 ⁿ			
Signed ICD	X										
Medical history	X										
Physical examination	X	X ^j					X ^j			X	
Vital Signs	X	X	X	X	X		X			X	
ECOG Performance Status	X	X					X			X	
Height	X										
Weight	X	X					X			X	
Hematology ^b	X	X	X	X	X		X			X	
Serum chemistry ^c	X	X	X	X	X		X			X	
Urinalysis ^d	X	X					X			X	
Beta-hCG for WCBP	X										
12-lead ECG	X	X ^e		X ^e			X ^e			X	
Concomitant medications	X						Continuous				
Adverse Event assessment							Continuous				
Bone Marrow Aspirate ^f	X					X		X	X		
Disease Response Assessment ^g	X					X		X	X		
Peripheral blood for PK assessment ^h		X		X							
Peripheral blood for PD (XMP) assessment ^h		X		X							
Administration of FF-10501-01 ⁱ		BID x 21 days					BID x 21 days				
Assessment of survival		X	X	X	X	X	X	X	X	X	X

^a Screening to be performed within 28 days of Cycle 1, Day 1

^b Hematology collected at Screening, Days 1, 8, 15 and 22 of Cycle 1, Day 1 of each subsequent cycle (within 3 days of Day 1 of each subsequent cycle) and End of Study. See **Table 7** for tests to be conducted at each time point.

^c Serum chemistry collected at Screening, Days 1, 8, 15 and 22 of Cycle 1, Day 1 of each subsequent cycle (within 3 days of Day 1 of each subsequent cycle) and End of Study. See **Table 7** for tests to be conducted at each time point.

^d Urinalysis collected at Screening, Day 1 of Cycle 1, Day 1 of each subsequent cycle (within 3 days of Day 1 of each subsequent cycle) and End of Study. See **Table 7** for tests to be conducted at each time point.

^e ECGs performed pre-dose and approximately 3 hours post-dose (following morning dose only)

^f Bone marrow aspirate required at Screening; at end of Cycles 1 and 3, every 2 cycles thereafter, and at relapse/progression, unless peripheral blood absolute count is $\geq 5.0 \times 10^9$ cells/L. See **Table 7** for tests to be conducted at each time point.

^g Disease Response Assessment may include bone marrow assessment, hematology for blood counts, physical exam, etc.

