3.4.3. Clinical Laboratory Results

Laboratory data will be listed by subject. Values above and below normal ranges will be indicated. All laboratory values will be graded according to the NCI-CTCAE version 4.03 criteria. Laboratory data will be summarized by actual value and change from baseline using number of non-missing observations, mean, standard deviation, median, minimum, maximum, and Grade 3 and 4 by dose cohort and by disease cohort treated at RP2D and schedule. In addition, shift tables will be presented.

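### Uric acid, one of three laboratory elevations the protocol reports for the same active ingredient, is not a scheduled test in Table 7

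*Protocol*

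**What the plan says.** The primary objective is "To determine the safety and tolerability in subjects who receive FF-10501-01 for the treatment of advanced hematologic malignancies" (protocol Section 2.1). Section 1.1 links the study drug to the older compound: "FF-10501-01 contains the same active pharmaceutical ingredient as SM-108".

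Protocol Section 1.3.1 summarises the SM-108 Phase 1 study, in which "73 patients were treated on a 5-day consecutive schedule at doses ranging from 20 to 2500" mg/m². Besides gastrointestinal events it reports "Elevated AST (to > 45 U), ALT (to > 50U) and uric acid" (uric acid to 8 mg/dL or more) in an unspecified number of patients.

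Protocol Section 7.1.10 defines the panel: "Clinical laboratory tests include hematology, serum chemistry, urinalysis and bone marrow aspirate". Table 7 lists the analytes. The hematology, chemistry, urinalysis and marrow footnotes to Appendix D send sites to Table 7 "for tests to be conducted at each time point", so Table 7 is the working test list at every visit.

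SAP Section 3.4.3 says "All laboratory values will be graded according to the NCI-CTCAE version 4.03 criteria", and protocol Section 8.3.1.2 has the same rule. The SAP adds no analyte to the protocol's list.

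**The concern.** A protocol that reports a laboratory effect of its own active ingredient, and has safety as its primary objective, would be expected either to measure that effect or to say why it does not. Here AST and ALT are followed and uric acid is dropped without comment.

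What is at stake is how the final report can be read. If hyperuricemia is absent from the laboratory tables, that will reflect the lack of a scheduled measurement and will not be evidence that uric acid stayed normal. The earlier observation came from 5 days of dosing. This trial doses for 14, 21 or 28 days per 28-day cycle and repeats the cycles, so the earlier data do not settle the question for this schedule.

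**Working it through.** The plan gives no figure to reproduce. The check sets the passages side by side and then adds a short illustrative calculation.

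**Step 1. Named signals against the panel.** The Table 7 serum chemistry column has 17 entries: creatinine, BUN, glucose, albumin, AST, ALT, LDH, total bilirubin, total protein, alkaline phosphatase, calcium, phosphorus, magnesium, sodium, potassium, chloride and bicarbonate.

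| Elevation named in Section 1.3.1 | In Table 7? |
|---|---|
| AST | Yes |
| ALT | Yes |
| Uric acid | No, in any column |

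Two of three are covered and one is not. Outside Section 1.3.1, uric acid appears nowhere in the protocol or the SAP.

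**Step 2. Other routes by which a value could reach the report.**
- *Adverse event recording (protocol Section 7.1.5).* Clinically significant laboratory changes are recorded as AEs, with stated exceptions. This needs a measured value first.
- *Local laboratories (protocol Section 10).* A site could run uric acid on its own initiative. Testing would then vary by site and subject, with no assured baseline.
- *Unscheduled results (SAP Section 2.3.1.1).* These are listed but left out of tabulations by visit.
- *CTCAE grading (SAP Section 3.4.3, protocol Section 8.3.1.2).* The rule covers all laboratory values, which can only mean values that were collected. SAP Section 2.3.2 does not impute missing data.

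Each route depends on someone choosing to test. None is a planned assessment.

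**Step 3. What scheduled testing could show (illustrative only).** The documents give no rate for uric acid elevation, so the 10% and 5% below are assumptions. The chance of at least one affected subject among n tested is 1 − (1 − p)^n.
- n = 20 (full Phase 2a cohort), p = 10%: 1 − 0.90^20 = 0.88.
- n = 20, p = 5%: 1 − 0.95^20 = 0.64.

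These are upper figures for the assumed rates. Protocol Section 3.1 lets Phase 1 subjects treated at the recommended dose and schedule count toward the 20, and plans 6 subjects there. If all 6 counted and none were tested, n = 20 − 6 = 14:
- p = 10%: 1 − 0.90^14 = 0.77.
- p = 5%: 1 − 0.95^14 = 0.51.

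Under the plan as written, the number of scheduled uric acid measurements is zero.

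**Step 4. The transpeptidase.** Table 2 in protocol Section 1.3.3 lists "Increased GTP" in 3 of 165 patients (3/165 = 1.8%). The abbreviation list gives GTP as glutamyl transpeptidase, and Table 7 omits it as well. At 1.8%, 20 tested subjects would show at least one case with probability 1 − (162/165)^20 = 0.31. This is a weak, secondary signal.

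**The case against.** The strongest reply is that this is a preference about panel content: nothing in the documents is contradictory and no stated analysis fails. The signal is thin. Section 1.3.1 gives no count for uric acid and calls the correlation between adverse events and dose unclear. Uric acid is absent from the adverse event table of the 165-patient study, the expected-event list in Section 7.1.6, the Japanese study summary and this trial's own interim summary. The Investigator's Brochure, which is not among these documents, may say more. All of this stands and limits the weight of the point. The later silence is weak reassurance, though, because the documents do not say whether uric acid was measured in those studies.

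Three stronger readings are tempting, and the documents do not support them.
- *That the trial could not detect or grade hyperuricemia at all.* The AE and local-laboratory routes exist, a recorded event would enter the TEAE tables, and the SAP does not restrict laboratory output to Table 7 analytes. The gap is in planned assessment.
- *That this trial doses higher than the study that produced the signal.* That study ran up to 2500 mg/m², while this trial's highest cohort received 1000 mg/m²/day. Only the longer duration is supported.
- *That adding the test would confirm or refute a drug effect.* There is no reference therapy, so the trial can describe frequency and change from baseline but cannot establish causation.

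The reply does not remove the omission. A named signal has no scheduled measurement and no stated reason for leaving it out.

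**Conclusion.** The point holds as a minor gap in safety ascertainment. One of the three laboratory elevations named in Section 1.3.1 has no scheduled measurement, so no planned assessment would detect, grade or tabulate hyperuricemia under this trial's longer dosing cycles. Any value that appears would come from unsystematic local testing.

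This conclusion rests on Table 7 being the complete scheduled list, as Appendix D indicates, and on no separate laboratory manual adding uric acid; neither document mentions one. The detection probabilities in the working only illustrate what testing would offer under assumed rates, and the conclusion does not depend on them. The transpeptidase, at 3 of 165, is optional and would not justify a change alone.

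**What to change.** Add uric acid to the Serum Chemistry column of Table 7 at the existing chemistry time points (Screening, Cycle 1 Days 1, 8, 15 and 22, Day 1 of each later cycle, and End of Study) for subjects still to be enrolled or still on treatment. Include it in the SAP Section 3.4.3 by-visit, change-from-baseline, shift and Grade 3/4 outputs. State in the SAP and the report that earlier subjects who were not tested are excluded from its denominators, and that subjects first tested while on treatment have no baseline and cannot enter the change or shift tables. The transpeptidase can be added in the same way if wanted. If the sponsor prefers not to test, one sentence in Section 7.1.10 giving the reason would answer the point.

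The cost is one analyte on samples already drawn, with no new visit or draw, plus a protocol amendment and a short SAP edit. The limitation that remains is the missing baseline for subjects already on study.
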